Protocol title: Comparison of Arm and Ankle Blood Pressure during Cesarean Delivery: A Blood Pressure Cuffs Pilot Study

NCT#: 2020H0502

IRB approval date: 14MAR2021

Comparison of Arm and Ankle Blood Pressure during Cesarean Delivery: A Blood Pressure Cuffs Pilot Study

BACKGROUND AND SIGNIFICANCE

A literature search found the incidence of hypotension after subarachnoid block (SAB) varied between 7.4% and 74.1%,^[1] while another recent publication discovered the incidence of hypotension to be 5.4%.^[2] There is a large variation of definitions used for intraoperative hypertension (IOH) in anesthesia literature. The relationship between these definitions and the incidence of IOH is depicted in Figure 1.^[3]

[figure not shown]

Figure 1. Incidences of hypotension after SAB and the definitions of hypotension

In the last three decades, numerous interventions have been studied and implemented into our daily practice, such as pre-loading versus co-loading, phenylephrine versus ephedrine, and phenylephrine infusion versus intermittent boluses. In addition, the effectiveness of left uterine displacement (LUD) to improve blood flow and pressure remains unclear. Also, there are issues to be addressed on this regard, including:

1. Poor placental perfusion from inadequate LUD due to the potential impact of supine hypotensive syndrome (SHS) secondary to aortocaval compression especially after SAB;
2. Shivering during cesarean delivery (CD) resulting in inaccurate BP measurements, the incidence of shivering during CD is reported to be 21.9%.^[4] It is unclear the impact of shivering during CD on blood pressure (BP) measurements;
3. Patient discomfort during BP measurements, calf > arm > ankle.^[5]

One study concluded there is poor correlation between arm and calf BP. They found calf BP was higher than arm BP, with an average difference in SBP of 18.3 ± 18.6 (95% CI: 14.0~22.6) before spinal anesthesia and

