14.2 ± 21.0 (95% CI: 9.4~19.1) before incision/after spinal, and average difference in MAP of 4.8 ± 11.8 (95% CI: 2.1~7.6) before spinal anesthesia and 0.1 ± 13.6 (95% CI: 2.1~7.6) before incision/after spinal anesthesia.^[6] In contrast, another study of healthy non pregnant volunteers demonstrated insignificant differences in average SBP differences (22.4 [95% CI: -2.7~47.4]) and average MAP differences (3.7 [95% CI: -12.3~19.7]) among both ankles and arm.^[5] A recent study reported the incidence of maternal systolic hypotension at 5 min post-SAB to be 16.7% in the LUD group and 53.3% in the non-LUD group.^[7] However, imaging findings have not existed in MRI studies with low risk parturients but possible at high-risk for SHS^[8, 9] who may benefit from LUD and other aggressive preventive measures to avoid undesired consequences.^[10, 11]

Nevertheless, none of studies have discussed issues related to SAB, LUD, SHS, and differences of between arm and ankle BP comprehensively. There are also the issues of sidedness of ankle BP measurements, as LUD tilts the body to the left side which may contribute to differences between arm and ankle BP.

Specific Aims

- To validate the effectiveness of LUD after SAB with simultaneous measurements of BP on the arm and left ankle during surgery in patients undergoing cesarean delivery (CD) at The Ohio State University Wexner Medical Center
- To determine whether ankle BP correlates more accurately than arm SBP with the incidence of nausea/vomiting and category II or III fetal heart tracing and bradycardia after SAB and LUD under no shivering conditions in patients undergoing C-Section at The Ohio State University Wexner Medical Center
- To determine the impact of body mass index and antepartum estimation of newborn weight on SHS^[12] after the SAB

MATERIALS AND METHODS

Location:

The OSUWMC Labor & Delivery

Null Hypothesis:

The magnitude of the differences in arm and ankle SBP is consistent before and after spinal anesthesia.

Study design:

A single center prospective self-control study.

Study population: eligibility will be determined by the inclusion/exclusion criteria specified below. After eligibility has been confirmed, data from up to 100 subjects will be enrolled.

Inclusion Criteria:

- a. Age ≥ 18 years old

- b. Women undergoing cesarean delivery at The Ohio State University Wexner Medical Center under spinal anesthesia
- c. American Society of Anesthesiologists Physical Status I-III

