- d. Body mass index during pregnancy $\geq 35 \text{ kg/m}^2$
- e. Able to consent in English language
- f. Singleton pregnancy

Exclusion criteria:

- a. Women undergoing elective cesarean delivery at The Ohio State University Wexner Medical Center under anesthesia other than spinal anesthesia (i.e. general and/or epidural anesthesia)
- b. Prisoners

Sample size:

For this pilot study, a sample size of 100 patients will offer valuable information on clinical outcomes for future randomized clinical trials on blood pressure monitoring in patients undergoing C-Section under SAB.

Outcomes:

- Primary outcome: difference of SBP measured between arm and ankle during elective CD before and after (pre-incision) SAB
- Secondary outcomes: incidence of nausea, vomiting and shivering, estimated blood lost, blood transfusion (e.g. packed red blood cells units), category II or III fetal heart tracing, fetal bradycardia, APGAR at 1 min and 5 min, neonatal intensive care unit admission rate, SBP differences between arm and ankle before and after LUD performed in before surgery and anesthesia (baseline), after spinal anesthesia, after the fetus delivered

Statistics:

Maternal and newborn parameters (e.g. age, weight, height, body mass index, gravida and parity, gestational age, newborn weight, and high-risk obstetrics factors), clinical parameters (e.g. degree of tilt, compression, and incidence of shivering) will be summarized using descriptive statistics (mean/standard deviation, median/IQR, frequencies/proportions) based on data characteristics.

In addition, descriptive statistics will be used to summarize differences between arm and ankle blood pressures taken at different time-points. Multivariable linear regression models will be used to evaluate associations between changes in the magnitude of difference in SBP/MAP measures from different time-points taking clinical factors such as degree of tilt, compression, shivering, and baby weight into account.

A Bland-Altman plot for arm and left ankle paired SBP taken during CD under spinal anesthesia will be created to identify bias and estimate 95% agreement limits.^[6, 14, 15, 16] SBP and MAP will be obtained at 6 data collection points preoperatively/pre-spinal with and without LUD, after SAB in supine position and LUD, and right after the fetus delivery in LUD, and supine after the delivery.

Data collection:

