1. Demographic data: age, weight, height, gestational age, newborn weight, HROB factors, locations of placenta, past medical history (i.e. cardiovascular disease), and circumferences of arm and ankle for BP measurements
2. Systolic and Mean Arterial Blood Pressure: measured concomitantly at different time points on arm (standard of care) and left ankle (research purposes)
 - a. Pre-spinal: supine and after LUD with 15° tilt ^[17] (≥ 1 measurement as required by standard of care)
 - b. Post-spinal: supine and after LUD (≥ 1 measurement as required by standard of care)
 - c. After delivery: supine and after LUD (≥ 1 measurement as required by standard of care)
 - d. Incidence of intraoperative shivering, nausea/vomiting, category II or III fetal heart tracing, fetal Bradycardia, intubation, and neonatal intensive care unit admission after cesarean delivery
3. Newborn's clinical variables documented in the medical records as standard of care (e.g. heart rate and APGARs at 1 min and 5 min)
4. Cord blood pH (if performed by standard of care)

Study procedures:

- Cuff size: large BP cuffs will be the default size for both arm and ankle measurements, but can be changed as clinically indicated based on circumferences of limbs
- Cuff location: BP cuffs will be placed on the contralateral arm to the main peripheral IV following standard procedures. Left ankle cuff will be placed underneath intermittent pneumatic compression cuffs
- Spinal anesthesia will be administered following standard of care anesthesia management for patients undergoing cesarean delivery at The OSUWMC
- Hypotension avoidance strategies (e.g. phenylephrine infusion beginning at 50 mcg/kg/min) will be implemented per anesthesia provider clinical criteria
- Fetal monitoring will be implemented as required by standard of care practices in patients undergoing cesarean delivery at The OSUWMC
- Ankle blood pressure monitor screen will be covered. Thus, anesthesia providers will not be able to make any clinical decisions based on ankle blood pressures but arm blood pressure (standard) instead.

ANTICIPATED IMPACT

Placement of BP cuffs on left ankle during CD after SAB may become standard of care and provide more comfort than the current standard of care. The difference between SBP or MAP in patients positioned supine and after LUD before SAB may become a simple method to identify parturients at high-risk for SHS and prevent perioperative complications.

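### Aim 1 claims to establish that left uterine displacement (LUD) works after spinal block, but the post-spinal supine-to-LUD change cannot be separated from time since block or vasopressor treatment

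*Combined protocol and SAP*

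**What the plan says.** The first of the Specific Aims is "To validate the effectiveness of LUD after SAB with simultaneous measurements of BP on the arm and left ankle during surgery". It does not name the measure by which effectiveness would be judged.

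Study design is "A single center prospective self-control study". Data collection item 2b gives "Post-spinal: supine and after LUD", and Statistics lists the same two post-spinal positions in the same order. Items 2a to 2c ask for at least one reading per position. They give no interval between readings and no rule for which reading counts if there are several.

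Under Outcomes, the LUD comparison is secondary: the arm-ankle SBP difference before and after LUD at baseline, after spinal anesthesia and after delivery. Statistics plans descriptive summaries of the arm-ankle differences, a Bland-Altman plot, and regression on changes in the difference, "taking clinical factors such as degree of tilt, compression, shivering, and baby weight into account".

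Under Study procedures, measures against hypotension are left to the anesthesia provider. The ankle screen is covered, so decisions rest on arm pressure. Background and Significance cites an LUD study that had a concurrent comparison, with systolic hypotension in "16.7% in the LUD group and 53.3% in the non-LUD group".

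**The concern.** The aim's wording is causal, and the design offers one post-spinal contrast to support it. If every woman is read supine first and in LUD second, the LUD reading always comes later after the block. Treatment may be given between the two, and it responds to arm pressure, which is one half of the arm-ankle outcome. Position, time and treatment then move together.

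At stake is what the pilot may conclude for Aim 1 and for the post-spinal part of the LUD secondary outcome. Because the pilot is meant to inform later randomized trials, an unsupported statement about LUD could be carried forward into their planning.

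**Working it through.** The plan gives no effect size, SD, alpha or power for the LUD contrast, so there is no planned figure to reproduce. The point rests on steps 1 and 2. Steps 3 and 4 are illustrations.

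**1. What the contrast contains.** Between the supine and LUD readings, let c be the drift (in mmHg) common to both limbs, a and k the extra drift in arm and ankle, and L_arm and L_ankle the LUD effects.
- Arm change = L_arm + c + a
- Ankle change = L_ankle + c + k
- Change in the arm-ankle difference = (L_arm − L_ankle) + (a − k)

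The common drift c cancels in the planned outcome; a − k does not. With one order for all women, the mean of a − k cannot be told apart from the LUD effect. A single-limb reading would also carry c, although Statistics specifies no single-limb analysis.

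**2. Whether the design supplies a second equation.** A reversed order in some women, a return to supine before delivery, or a concurrent non-LUD group would do so. None is described. The pre-spinal supine/LUD pair (item 2a) is free of time since block, but it describes unblocked women. The after-delivery pair has no fetus in the uterus. Its order also conflicts: LUD then supine in Statistics, supine then LUD in item 2c.

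**3. Scale (illustration).** Background and Significance cites an arm-calf "average difference in SBP of 18.3 ± 18.6 (95% CI: 14.0~22.6) before spinal anesthesia" and "14.2 ± 21.0 (95% CI: 9.4~19.1) before incision/after spinal".
- Shift = 18.3 − 14.2 = 4.1 mmHg.
- Implied n: the CI half-widths are (22.6 − 14.0)/2 = 4.3 and (19.1 − 9.4)/2 = 4.85. Solving t × SD/√n for n gives about 74 both times.
- SD of the shift = √(18.6² + 21.0² − 2ρ × 18.6 × 21.0) = 19.9 (ρ = 0.5) or 15.5 (ρ = 0.7). The 95% CI is 4.1 ± 4.6 = −0.5 to 8.7, or 4.1 ± 3.6 = 0.5 to 7.7.

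This reference concerns the calf, spans before to after spinal rather than two post-spinal readings, and may be zero. It is not a bound.

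Now assume n = 100, SD 21.0, ρ = 0.5 or 0.7, no LUD effect, and a two-sided 5% paired t-test. SD of change = 21√(2(1 − ρ)) = 21.0 or 16.3, so SE = 2.10 or 1.63. The chance of p<0.05 (noncentral t) is:

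| Limb-specific drift (mmHg) | ρ = 0.5 | ρ = 0.7 |
|---|---|---|
| 0.5 | 5.6% | 6.1% |
| 1 | 7.6% | 9.3% |
| 2 | 15.6% | 23.0% |
| 4.1 | 48.9% | 70.4% |

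**4. Adjusting for time (illustration).** Fit change = position + slope × gap, with one reading per position and gaps assumed uniform over 2 to 5 min (mean 3.5, variance 9/12 = 0.75).
- Within-woman correlation of position and time = 3.5/√(3.5² + 0.75) = 0.97.
- SE inflation = √(1 + 3.5²/0.75) = 4.16. The 95% half-width rises from about 3 to 4 mmHg to about 13 to 17 mmHg.
- With two readings per position at the same spacing and independent errors, the correlation is about 0.88 and the inflation about 2.1.

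**The case against.** The strongest reply is that the plan never sets out to test LUD. Its only null hypothesis concerns before versus after spinal, the LUD contrast is secondary, and the analyses are descriptive or about association. This largely stands. A reader might infer that the pilot will declare LUD effective, but Statistics contains no LUD test, so the false-positive rates above belong to an analysis the plan does not name. What survives is the aim itself, which promises a conclusion that those analyses cannot deliver.

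Second, reading both limbs at once removes common drift. This is correct, and it narrows the concern to limb-specific drift. Stability of the difference across the block cannot be assumed, however, because that is the study's own null hypothesis.

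Third, a reader might infer that times and vasopressor will go uncollected because Data collection omits them. The documents do not show that. The list is not exhaustive: blood loss, transfusion and compression appear under Outcomes or Statistics and are also missing from it. The covariate list is open-ended too. The omission is a reason to name the items, not evidence that they will be lost.

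Fourth, near-collinearity of time and position depends on one reading per position, and the plan allows more. Adjustment would be costly, by a factor of about two to four in the SE under step 4's assumptions, but not shown to be useless.

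**Conclusion.** The point holds as a mismatch between Aim 1 and the design: a post-spinal supine-to-LUD change cannot be attributed to LUD rather than to time since block or treatment. In the planned arm-ankle difference, the residual bias is limb-specific and of unknown size. It could be negligible (0.5 mmHg leaves the illustrative error rate near 6%) or material. The conclusion needs only that the listed post-spinal order is the order carried out; it does not rest on the assumed drift, correlations or gaps.

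Three further readings go beyond the documents. One is that the pre-spinal order is contradictory: the phrase in Statistics about readings with and without LUD states no sequence, so only the after-delivery order conflicts. Another is that the primary outcome is untouched. The lack of control over LUD does not bear on it, but the unstated reading rule and unlisted vasopressor do affect the before/after-spinal comparison. The third is that results must be reported by arm side. The arm cuff's side can vary with the IV, but nothing in the documents sizes an effect of this or justifies a subgroup report.

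The change is worth making before analysis; the point does not invalidate the pilot.

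**What to change.** 1. Restate Aim 1 as describing the change in arm and ankle pressure from supine to LUD, and state that the post-spinal change will not be attributed to LUD.
2. Add to Data collection the times of the block, of each position change and of each reading, and any vasopressor given between readings. State which reading represents a position when more than one is taken; this also serves the primary before/after-spinal outcome. Label any analysis adjusted for time or vasopressor as exploratory, because time tracks position closely and treatment responds to arm pressure.
3. Reconcile the after-delivery order of positions between Statistics and Data collection item 2c.

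The cost is a few extra data fields per woman and a more modest aim. None of these changes alters clinical management.

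### Shivering is listed only as an intraoperative incidence, but the second aim and the regression need to know whether the woman was shivering at each blood pressure reading

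*Combined protocol and SAP*

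**What the plan says.** Background and Significance lists among the open problems "Shivering during cesarean delivery (CD) resulting in inaccurate BP measurements". It cites an incidence of 21.9% and adds that the effect of shivering on blood pressure measurement is unclear.

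Shivering is described as an incidence in three places:
- Outcomes: "Secondary outcomes: incidence of nausea, vomiting and shivering, estimated blood lost".
- Statistics, descriptive summaries: "clinical parameters (e.g. degree of tilt, compression, and incidence of shivering".
- Data collection, item 2d: "Incidence of intraoperative shivering, nausea/vomiting, category II or III fetal heart tracing, fetal Bradycardia, intubation", on the same line as neonatal intensive care admission.

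Two planned analyses use shivering:
- The second specific aim compares how well ankle and arm pressure track nausea/vomiting and fetal heart events "after SAB and LUD under no shivering conditions".
- The regression in Statistics models how the arm-ankle difference changes between time points, "taking clinical factors such as degree of tilt, compression, shivering, and baby weight into account".

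Paired pressures are taken at six points: pre-spinal, post-spinal and after delivery, each supine and with left uterine displacement (LUD). The primary outcome compares the arm-ankle difference before and after the subarachnoid block (SAB), with the second value taken before incision.

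**The concern.** If shivering spoils a pressure reading, it does so while that reading is being taken. A single entry covering the operation cannot separate a woman who was shivering at her post-spinal reading from one who first shivered after delivery. The two analyses that use shivering both need that separation.

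For the second aim, the analyst could not tell which readings meet the stated condition. For the regression, the analyst would have one fixed value for a state that can differ between the time points being compared. For a woman who starts shivering late, that value would attach a later event to a change already complete. Shivering status that nobody notes at the reading may not be recoverable at analysis, so this has to be settled in data collection.

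**Working it through.** **Need against record**

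| Use of shivering | What it needs | What is listed |
|---|---|---|
| Secondary outcome | Whether the woman shivered | Incidence: sufficient |
| Second aim | Status at the readings after SAB and LUD | Incidence only |
| Regression across time points | Status at the readings forming each contrast | Incidence only |
| Primary outcome, Bland-Altman plot | No shivering condition stated | Not applicable |

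**Inputs**
- Women: 100 (Sample size; enrolment is up to that number).
- Shivering incidence: 0.219 (Background, from a cited study).
- Paired readings per woman: 3 phases × 2 positions = 6, which matches the count in Statistics.
- q, the share of ever-shivering women who are shivering at the post-spinal, pre-incision reading: not given, so taken over its whole range, 0 to 1.

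The protocol gives no figure of its own on this point to reproduce.

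**Women flagged.** 100 × 0.219 = 21.9, about 22.

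**Flagged women whose post-spinal, pre-incision reading was unaffected.** 21.9 × (1 − q):
- q = 1: 0
- q = 0.5: 10.95, about 11
- q = 0: 21.9, about 22

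**Dilution of the coefficient.** Suppose shivering shifts the post-spinal arm-ankle difference by b, and the pre-spinal readings are unaffected. The mean shift is q × b among flagged women and 0 among the rest. An ever-shivered flag therefore estimates q × b instead of b. With b = 10 mmHg (an assumption, for illustration only), a simulation of 2,000,000 women with a residual SD of 15 mmHg (also assumed) agrees:

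| q | q × b (mmHg) | Simulated coefficient (mmHg) |
|---|---|---|
| 0 | 0 | 0.0 |
| 0.25 | 2.5 | 2.5 |
| 0.5 | 5.0 | 5.0 |
| 0.75 | 7.5 | 7.5 |
| 1 | 10 | 10.0 |

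In this model the unflagged women contain nobody who shivered, so their mean change is undisturbed. What suffers is the shivering coefficient.

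**If the flag were used to exclude women.** The protocol does not prescribe this; the count only shows how blunt the flag is. Across all readings, 21.9 × 6 = 131.4 of 600 pairs would go. If each flagged woman shivered at k of the six points, the unaffected pairs among those removed would be 21.9 × (6 − k): 109.5 for k = 1, 87.6 for k = 2 and 65.7 for k = 3. A record at each reading would set aside only 21.9 × k: 21.9, 43.8 or 65.7 pairs.

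**The case against.** The strongest reply is that the protocol never says shivering is recorded once per woman. An incidence is a way of summarising an event and does not fix how it is recorded. Item 2d also sits under a heading about measurements at several time points, and the Risks section has researchers collecting pressures during surgery, so they could note timing. The case report form is not among the documents. This stands as far as it goes: the per-woman unit is an inference. It is still the more natural reading, because the line also carries once-per-case events such as intubation and neonatal intensive care admission. If recording at each reading is intended, the protocol needs to say so.

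A reader might go further and infer that the plan discards valid readings, including primary pairs. The documents do not support that. No rule excludes women who shiver at any time, and the wording of the second aim most naturally describes conditions when the pressure is taken. The shivering restriction appears only in that aim. It is absent from the primary outcome, the null hypothesis, the descriptive summaries of arm-ankle differences and the Bland-Altman plot.

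Nor is the regression confined to changes before incision. It spans several time points, including after delivery, where later shivering is relevant. Its covariate list is illustrative and the coding of shivering is left open. The effect shown is dilution of one coefficient in a largely descriptive pilot, and no bias in the arm-ankle change itself has been shown.

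**Conclusion.** The gap is real but limited. Two planned analyses depend on shivering status at the reading, and the protocol lists no variable that supplies it and no definition of the condition in the second aim. With the listed variable alone, that condition cannot be applied to the readings it concerns. An ever-shivered flag would also understate any shivering effect in contrasts completed before shivering began, including pre-spinal to post-spinal. As written, no primary pair is lost.

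About 22 of 100 women would be flagged, and for 0 to 22 of them the post-spinal, pre-incision reading was unaffected. The documents give nothing to narrow that range. The 22 assumes full enrolment and that the cited 21.9% carries over to this cohort, which is restricted to a body mass index of at least 35 kg/m². The size of any artefact is unknown; the 10 mmHg above is illustrative only. This is a cheap improvement to make before data are collected, because the information may not be recoverable afterwards.

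**What to change.** - **Data collection, item 2:** add a yes/no tick for shivering at each of the six paired readings.
- **Second aim:** state that its condition is met by readings ticked as no.
- **Statistics:** state that the regression covariate is shivering at the readings that form each contrast.
- **Outcomes:** keep the per-woman incidence as the secondary outcome; it can be reported alongside the ticks.

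The cost is one tick per reading by researchers who already collect the pressures, a few sentences in the protocol and a slightly longer case report form. Patient care is unchanged.

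### The example phenylephrine rate in the study procedures, 50 mcg/kg/min, comes to milligrams per minute at any adult weight; delete the number, or verify its unit if it is kept (minor)

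*Combined protocol and SAP*

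**What the plan says.** The statement is a bullet under Study procedures, in Materials and Methods: "Hypotension avoidance strategies (e.g. phenylephrine infusion beginning at 50 mcg/kg/min) will be implemented per anesthesia provider clinical criteria". It is the only drug rate in the documents.

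Three other places bear on it:

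- Inclusion criterion d sets "Body mass index during pregnancy" at 35 kg/m² or more, so participants are selected for high BMI. Inclusion criterion a limits entry to adults: "Age ≥ 18 years old".
- The Data collection list includes weight and height among the items to record ("Demographic data: age, weight, height, gestational age, newborn weight, HROB factors"), but no height or weight value appears anywhere.
- Background and Significance lists "phenylephrine versus ephedrine, and phenylephrine infusion versus intermittent boluses" among interventions studied and taken into daily practice. It gives no rate.

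The documents name no dosing weight (actual, ideal or other), no maximum rate, no titration rule and no concentration. They cite no source for the 50 mcg/kg/min figure. One reference has a phenylephrine infusion in its title, but it is cited in the Background for preventive measures in general, not for this rate.

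**The concern.** The example is written in micrograms per kilogram per minute for women who must have a BMI of at least 35 kg/m². Multiplied out, it becomes a vasopressor rate in milligrams per minute. That raises the question whether the per-kilogram term belongs there.

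The line also stands in the operative procedures rather than in background text. If anyone set an infusion from the printed figure and the unit was wrong, a pregnant patient would bear the consequence. Even if the unit is right, the figure does not define one rate, because the dosing weight is not stated.

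**Working it through.** The plan makes no calculation here, so there is no derived figure to reproduce. The check only converts the printed rate to an absolute one.

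**Inputs**

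- Rate: 50 mcg/kg/min (Study procedures).
- BMI: 35 kg/m², the entry minimum (Inclusion criteria, item d).
- Height: assumed 1.45 to 1.75 m, with 1.40 to 1.80 m as a wider range.
- Dosing weight: assumed to be actual body weight.

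**Formulas**

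- Weight (kg) = BMI × height².
- Absolute rate (mg/min) = 50 × weight / 1,000.

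**Step 1: a bound that does not depend on the assumptions.** The rate passes 1 mg/min when weight exceeds 1,000 / 50 = 20 kg. At BMI 35, a weight of 20 kg would mean a height of √(20/35) = 0.76 m. No adult falls below this, whichever dosing weight is used.

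**Step 2: the rate at BMI 35.**

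| Assumed height (m) | Weight (kg) | Rate (mg/min) |
|---|---|---|
| 1.40 | 35 × 1.40² = 68.6 | 3.43 |
| 1.45 | 35 × 1.45² = 73.6 | 3.68 |
| 1.60 | 35 × 1.60² = 89.6 | 4.48 |
| 1.75 | 35 × 1.75² = 107.2 | 5.36 |
| 1.80 | 35 × 1.80² = 113.4 | 5.67 |

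This gives about 3.7 to 5.4 mg/min over the main range and 3.4 to 5.7 mg/min over the wider one. BMI 35 is the minimum, so a heavier woman of the same height would receive more.

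**Step 3: sensitivity to the dosing weight.** At an assumed height of 1.60 m:

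- A reference weight at BMI 25 (illustrative) is 25 × 1.60² = 64 kg, giving 3.2 mg/min.
- Actual weight at BMI 50 (illustrative) is 50 × 1.60² = 128 kg, giving 6.4 mg/min.

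The choice of dosing weight moves the figure, but it stays in milligrams per minute.

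**The case against.** The strongest objection is that no error is shown. No second phenylephrine rate, ceiling or total dose in the documents conflicts with 50 mcg/kg/min, and no safe or usual dose is given against which to call it too high. That stands. The documents alone cannot settle the unit, which is why the point is limited to deleting or verifying the number.

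A reader might infer that the per-kilogram term is a demonstrated slip and that the rate is overstated about 74 to 107 times. The documents do not support this. That factor is simply body weight in kilograms at the assumed heights. It would arise for any per-kilogram dose and is not evidence that the term was unintended.

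It can also be said that the number directs no one's treatment. It is introduced as an example and deferred to the provider. Phenylephrine is not a study intervention, and the covered ankle monitor means that "anesthesia providers will not be able to make any clinical decisions based on ankle blood pressures but arm blood pressure (standard) instead". The Risks section recognises only a breach of confidentiality. All this is fair and keeps the severity low. It does not argue for keeping the figure: if providers ignore it, deletion loses nothing, and if someone relies on it, the unit has to be right.

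Finally, the 3.7 to 5.4 mg/min range depends on assumed heights and on actual-weight dosing. That is also true, but the 20 kg bound depends on neither.

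**Conclusion.** The point holds as a minor patient-safety query with an inexpensive remedy. As printed, the example rate exceeds 1 mg/min for any adult. It is about 3.7 to 5.4 mg/min at BMI 35 if heights are 1.45 to 1.75 m and dosing is on actual body weight. Nothing elsewhere in the documents supports, caps or explains it.

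A unit error is suspected only. If the per-kilogram term was intended, there is no unit error, although the dosing weight is still undefined. Whether a rate of this size is clinically acceptable is for the site's anesthesia team to confirm, since the documents give no benchmark. The primary and secondary outcomes, the choice of 100 patients and the planned analyses are unaffected.

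**What to change.** Delete the starting rate from the parenthesis, so that the bullet names phenylephrine infusion as the example and leaves the rest to the provider's criteria as now. This matches the neighbouring bullets on spinal anesthesia and fetal monitoring, which give no doses. If the investigators prefer to keep a rate, they should first verify its unit against local practice and, if it is per kilogram, state which body weight applies. The change should go through whatever IRB route the site requires.

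The cost is one edited line and the associated IRB paperwork. It needs no additional patients, staff or procedures.
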